#### Outcome Measure #3: Procedural success at 30 days

Procedural success is defined as:

- Device success at 30 days, and
- None of the following device- or procedure-related serious adverse events:
  - o Life-threatening major bleed
  - Major vascular or cardiac structural complications required unplanned reintervention or surgery
  - Stage 2 or 3 acute kidney injury (AKI) (includes new dialysis)
  - o Pulmonary embolism
  - Severe heart failure (HF) or hypotension requiring IV inotrope, ultrafiltration, or mechanical circulatory support
  - Prolonged intubation >48 hours

The analysis cohort for procedural success will be the attempted implant cohort. The percentage of subjects with procedural success will be presented. If an element of the composite is missing and available elements meet the success criteria, the subject will be excluded from the analysis.

#### Outcome Measure #4: Freedom from TPV dysfunction out to 5 years

TPV dysfunction is defined as any one of the following:

[figure not shown]
- RVOT reoperation for device-related reasons
- Catheter re-intervention of TPV
- Hemodynamic dysfunction of the TPV (moderate or greater pulmonary regurgitation, and/or a mean RVOT gradient > 40 mmHg)

The analysis cohort will be the implanted > 24 hours cohort. The endpoint will be described by Kaplan-Meier statistics. The loglog transformed two-sided 95% confidence interval using the Peto standard error at 6 months (183 days), 1 year (365 days), 2 years (730 days), 3 years (1095 days), 4 years(1460 days) and 5 years (1825 days) will be presented.

This document is electronically controlled **Medtronic Controlled Information** 056-F286, Statistical Analysis Plan Template Version A

Revision 5.1

Page 20 of 24

#### Outcome Measure #5: Assessment of safety

Detailed information about how adverse events will be summarized is delineated in section 7.10.

# Outcome Measure #6: Characterization of right ventricle remodeling following TPV implant as assessed via CMR

Summary statistics by visit interval will be provided for the following measures at pre-implant, 6 months post-implant, and 2 to 5 years post-implant.

- Right Ventricular End Diastolic Volume (RVEDV)
- Left Ventricular End Diastolic Volume (LVEDV)
- Right Ventricular End Diastolic Volume Index (RVEDVi)
- Left Ventricular End Diastolic Volume Index (LVEDVi)
- Right Ventricular End Systolic Volume (RVESV)
- Light Ventricular End Systolic Volume (LVESV)
- Pulmonary Regurgitation Fraction (PRF)
- Right Ventricular Ejection Fraction (RVEF)
- Left Ventricular Ejection Fraction (LVEF)
- Net Right Ventricular Stroke Volume
- Net Left Ventricular Stroke Volume
- Right ventricular to left ventricular end-diastolic volume ratio

The analysis cohort will be implanted longer than 24 hours cohort. Summary statistics such as mean, standard deviation, median, minimum, maximum, first and third quartiles will be provided for continuous variables and count and percentage will be provided for categorical variables.

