## 8. Study Procedures

### 8.1. Schedule of Events

Evaluation / Visit	Pre-Implant	Implant 	Discharge	1 Month	6 Months	1 Year	Annual (2-5 Years)
Visit Window	Within 24 weeks prior to Implant procedure unless otherwise specified	Implant procedure date	Prior to hospital discharge, or at 30 days post-implant if subject remains hospitalized	Between 2 and 6 weeks after implant	Between 23 and 29 weeks after implant date	Between 44 and 60 weeks after implant date	Between ±8 weeks after the implant anniversary date
Informed Consent	X						
Screening Committee Review	X						
Clinical Assessment	X		X	X	X	X	X
TPV Implant		X					
Echo	X 		X	X	X	X	X
Functional Cardiac Magnetic Resonance Imaging	X 			X 	X		To be completed at 2 & 5 Year Follow-Up
CT Cardiac Angiography	X 		X 				
Fluoroscopy		X		X	X	X	To be completed at 5 Year Follow-Up
Chest X-Ray			X				
SF-36	X 			X	X	X	X
Assessment of Adverse Event/ Device Deficiency	X	X	X	X	X	X	X

 Post-procedure care is carried out according to the standard care of the interventional cardiologist at his/her discretion.

 Clinical Assessment includes: at baseline – subject demographic, medical history, and medication assessment; at follow-up - medication assessment, review of adverse events, and device deficiencies.

 If an echo exam has been performed for routine diagnostic purposes prior to consenting, it can be used as the pre-implant echo exam, provided it was performed within 24 weeks prior to implant. The Principal Investigator must determine if the exam contains the protocol-required data and remains adequate for subject evaluation. If subject is screen failed, functional CMR imaging was used to satisfy the inclusion criteria, and pre-implant echo was not completed within window, a deviation is not required.

 If CMR imaging is contraindicated (e.g., subject has implantable cardiac rhythm device), no deviation will be required for MRI not performed.

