### Characterization of right ventricle remodeling following TPV implant as assessed via CMR

Right ventricle remodeling will be assessed via CMR at pre-implant, 6 months post-implant, 2 years post-implant, and 5 years post-implant. The analysis cohort will be implanted longer than 24 hours cohort. Summary statistics such as mean, standard deviation, minimum, median, and maximum will be provided for continuous variables and count and percentage will be provided for categorical variables.

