#### 5. Investigation Plan

This is a prospective, non-randomized, multi-center study, with each center following a common protocol. Up to 40 subjects will be implanted at up to 15 centers in the United States, Canada, and Japan. It is anticipated that more than 40 subjects will be enrolled (i.e. consented) to meet the target of up to 40 implants as not all subjects will be suitable for implantation. No site shall implant more than 10 subjects., excluding roll-in subjects. Subjects who discontinue participation prematurely following implant will be included in the analysis of results (as appropriate) and will not be replaced in the enrollment of total study subjects implanted. All implanted subjects will receive the Harmony™ TPV, either size 22 or 25. Each implanted subject will be followed for five years or until the subject's Harmony™ TPV is explanted. Subjects who failed the first screen for the TPV 22 device before the second device size TPV 25 were introduced, will either exit from the study or rescreen for the second device size later when TPV 25 device is available. All subjects who are rescreening for the new valve size TPV 25 will have all baseline assessments performed for TPV 25.

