#### 7.4 Handling of Missing, Unused, and Spurious Data and Dropouts

Every effort will be undertaken to minimize missing data. In time-to-event outcomes drop-outs will be censored at the time of discontinuation, consistent with the Kaplan-Meier approach.

Unless otherwise specified in each objective, no statistical techniques will be used to impute missing data for continuous or categorical outcomes. If a subject's data are missing for any reason, that subject will not be included in that portion of the analysis. The number of subjects included in each analysis will be reported so that the reader can assess the potential impact of missing data.

In the case of partial dates, if only the month and year are known, the event or assessment will be analyzed as if it occurred on the 15th of that month. If only the year is known, the event or assessment will be analyzed as if it occurred on June 30th of that year. These resolutions of partial dates are subject to the restrictions that pre-procedure assessments must occur between the enrollment date and the procedure date or within the window defined in the CIP. The post-procedure events and assessments must occur no earlier than the procedure date. According to the section 6.1 of the CIP, the windows for pre-procedure assessments are:

- CMR exam (functional): within 52 weeks prior to the implant date
- Clinical evaluation: within 24 weeks prior to the implant date

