#### 7.12 Health outcomes

#### Outcome Measure #7: Characterize quality of life scores over time

Quality of life will be assessed by the subjects completing the RAND 36-Item Short Form (SF-36) questionnaire. Completion of the SF-36 questionnaire is required at the following intervals: pre-implant, 1-month post-implant, 6 months post-implant, and annually post-implant out to 5 years. The analysis cohort will be the implanted >24 hours cohort.

Summary statistics such as mean, standard deviation, minimum, median, and maximum will be provided for quality of life scores over time as assessed by the SF-36 at pre-implant, 1-month post-implant, 6 months post-implant, and annually post-implant out to 5 years.

The responses will be scored by using the 36-Item Short Form Survey (SF-36) Scoring Instructions published by Rand Corporation [2]. The scoring is a two-step process as described in Table 1 and Table 2:

Revision 5.1 Page 21 of 24

[figure not shown]

Table 1. Step 1: Recoding Items

Item numbers	Change original	To recoded
	response category *	value of:
1, 2, 20, 22, 34, 36	1 →	100
	2 →	75
	3 →	50
	4 →	25
	5 →	0
3, 4, 5, 6, 7, 8, 9, 10, 11, 12	1 →	0
	2 →	50
	3 →	100
13, 14, 15, 16, 17, 18, 19	1 →	0
	2 →	100
21, 23, 26, 27, 30	1 →	100
	2 →	80
	3 →	60
	4 →	40
	5 →	20
	6 →	0
24, 25, 28, 29, 31	1 →	0
	2 →	20
	3 →	40
	4 →	60
	5 →	80
	6 →	100
32, 33, 35	1 →	0
	2 →	25
	3 →	50
	4 →	75
	5 →	100

\* Pre-coded response choices as printed in the questionnaire.

Revision 5.1 Page 22 of 24

[figure not shown]

Table 2. Step 2: Averaging Items to Form Scales

Scale	Number of items	After recoding per Table 1,
		average the following items
Physical functioning	10	3 4 5 6 7 8 9 10 11 12
Role limitations due to physical health	4	13 14 15 16
Role limitations due to emotional problems	3	17 18 19
Energy/fatigue	4	23 27 29 31
Emotional well-being	5	24 25 26 28 30
Social functioning	2	20 32
Pain	2	21 22
General health	5	1 33 34 35 36

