Table 1 shows that responses 1 through 5 for item 20 should be recoded to values of 100, 75, 50, 25, and 0, respectively. Responses 1 through 5 for item 32 should be recoded to values of 0, 25, 50, 75, and 100, respectively. Table 2 shows that these two recoded items should be averaged together to form the social functioning scale. If the respondent is missing one of the two items, the person's score will be equal to that of the non-missing item. The scale for each of 8 domains will be calculated respectively and will be counted as the quality of life score.

Summary statistics for continuous variable will be provided for the quality of life scores at pre-implant, 1-month post-implant, 6 months post-implant, and annually post-implant out to 5 years.

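### RV remodeling and SF-36 are planned only as visit-by-visit summaries, so the tables give no valid interval for change and visit means may rest on different subjects

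*SAP*

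**What the plan says.** **RV remodeling.** SAP 7.11, Outcome Measure #6: "Summary statistics by visit interval will be provided for the following measures at pre-implant, 6 months post-implant, and 2 to 5 years post-implant". The set is the implanted > 24 hours cohort ("The analysis cohort will be implanted longer than 24 hours cohort"), with no restriction to subjects who have both a baseline and a follow-up scan. The planned statistics are mean, SD, median, quartiles, minimum and maximum. Protocol 12.3 names the visits separately: "Right ventricle remodeling will be assessed via CMR at pre-implant, 6 months post-implant, 2 years post-implant, and 5 years post-implant".

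**Quality of life.** SAP 7.12, Outcome Measure #7: "Summary statistics such as mean, standard deviation, minimum, median, and maximum will be provided for quality of life scores over time". After the scoring rules it repeats the plan: "Summary statistics for continuous variable will be provided for the quality of life scores at pre-implant", and then at each later visit. Protocol 12.3 says the same.

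**Who contributes at each visit.**
- SAP 7.4: "If a subject's data are missing for any reason, that subject will not be included in that portion of the analysis". There is no imputation unless an objective specifies it. The number of subjects in each analysis is to be reported.
- SAP section 5: "Each implanted subject will be followed for five years or until the subject's Harmony™ TPV is explanted".
- Protocol 8.1, footnote on CMR: "If CMR imaging is contraindicated (e.g., subject has implantable cardiac rhythm device), no deviation will be required for MRI not performed".

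The current text of both documents contains no change from baseline, paired set, confidence interval for change or repeated-measures model for either outcome. The SAP version history records that a mixed model for Outcome #6 was removed. That is superseded text and not an error in itself, but no other within-subject analysis took its place.

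**The concern.** Remodeling after implant and quality of life over time are questions about change within a person. The planned tables describe a group of people at each visit, and two things follow.

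First, the groups can differ between visits. A subject who is explanted, leaves the study, or can no longer have CMR stays in the pre-implant summary and drops out of later ones. Explant in particular is plausibly related to how the valve and ventricle are doing. The means can then move although no ventricle has changed.

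Second, the natural result to report is a mean change with its interval, and the tables do not supply one. The standard error of a change depends on the correlation between a subject's two measurements, which visit-level means and SDs do not contain.

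At stake is how readable and how precisely stated two descriptive additional outcomes are. No success criterion depends on them.

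**Working it through.** **Inputs.** The documents give no SD, within-subject correlation, dropout rate, CMR contraindication rate or target change for these outcomes, so there is no plan figure to reproduce. From the documents: 40 subjects in the pivotal cohort (SAP section 6). Assumed: correlation rho of 0.5 to 0.8 between visits; equal SDs at both visits; 10% to 40% missing at follow-up; a baseline difference of 0.5 SD between missing and remaining subjects. Results are in SD units, with n0 subjects at baseline and n1 of the same subjects at follow-up. The standard errors also assume that missingness is unrelated to the values.

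**Step 1: shift from composition alone.** Let a fraction m be missing later, with those subjects differing at baseline by d from those who remain. If nobody changes, the baseline mean differs from the follow-up mean by m × d. With d = 0.5:

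| m | shift (SD) |
|---|---|
| 10% | 0.05 |
| 20% | 0.10 |
| 30% | 0.15 |
| 40% | 0.20 |

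With complete data the shift is zero.

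**Step 2: three standard errors.**
- A: visits treated as independent samples, which is all the planned tables allow: sqrt(1/n0 + 1/n1).
- B: true SE of the difference between the two visit means: sqrt(1/n0 + 1/n1 − 2·rho/n0).
- C: SE of the mean paired change: sqrt(2(1 − rho)/n1).

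**Step 3: complete data, n0 = n1 = 40.** B and C are identical, because the difference of means is the mean of the differences. A/C = 1/sqrt(1 − rho).

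| rho | A | B = C | A/C | 95% half-width, A | 95% half-width, C |
|---|---|---|---|---|---|
| 0.5 | 0.224 | 0.158 | 1.4 | 0.445 | 0.320 |
| 0.7 | 0.224 | 0.122 | 1.8 | 0.445 | 0.248 |
| 0.8 | 0.224 | 0.100 | 2.2 | 0.445 | 0.202 |

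Half-widths use t quantiles with 78 df (A) and 39 df (C).

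**Step 4: n0 = 40, n1 = 30.**

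| rho | B | C | C smaller than B by |
|---|---|---|---|
| 0.5 | sqrt(0.0583 − 0.0250) = 0.183 | sqrt(1.0/30) = 0.183 | 0% |
| 0.7 | sqrt(0.0583 − 0.0350) = 0.153 | sqrt(0.6/30) = 0.141 | 7% |
| 0.8 | sqrt(0.0583 − 0.0400) = 0.135 | sqrt(0.4/30) = 0.115 | 15% |

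In general C² − B² = (1/n1 − 1/n0)(1 − 2·rho). Pairing therefore gains only above rho = 0.5, and costs a little below it.

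**Check.** In 20,000 simulated trials with rho = 0.7 and 32 of 40 followed, B was 0.146 and C was 0.136. The formulas give 0.146 and 0.137.

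**The case against.** The strongest reply is that a reader might infer that the plan throws away precision: 1 − sqrt(1 − rho) suggests a paired SE 29% to 55% smaller for rho 0.5 to 0.8. That reading does not stand. It compares C with A, as though the visits were separate samples, when they are the same people. Against the true SE of the difference of visit means, pairing gains nothing with complete data and 0% to 15% with 30 of 40 followed. What stands is that the reader of the tables can compute only A.

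Several other points have weight:
- **Composition.** The documents do not establish that the baseline mean uses every subject. Someone already contraindicated for CMR at baseline is absent from both means and shifts nothing. The amount of missing data is unknown, and SAP 7.4 requires the number analysed to be reported. That number shows how many are missing, though not whether they differed at baseline.
- **Denominator.** Forty is illustrative. The mTPV 25 cohort (up to 15) is pooled in for the 5-year analyses, and remodeling is also analysed together with the early feasibility study (n = 20).
- **Freedom to add analyses.** SAP section 3 expects analyses beyond the plan, and the lists of statistics are open-ended. Paired change is thus permitted, but it is not pre-specified.
- **The 2-to-5-year wording.** A reader might infer that the two later scans are merged into one summary. The documents do not show this. The SAP sentence says summaries are by visit interval, and the protocol schedule uses a similar column label while placing CMR at years 2 and 5 only. It is an ambiguity to clear up.

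**Conclusion.** The point holds as a gap in reporting. Both outcomes concern change, and the plan tabulates only visit-level summaries among subjects with data at each visit. Two consequences follow:
- No valid interval for change can be derived from the tables. A reader who treats visits as independent overstates the SE about 1.4 to 2.2 times with complete data, at assumed rho of 0.5 to 0.8.
- Visit means may be compared across partly different subjects. The illustrative shift is 0.05 to 0.20 SD, which rests on an assumed missing fraction and an assumed baseline difference of 0.5 SD.

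The absence of a paired summary is certain from the text. The sizes depend on inputs the documents do not give.

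A reader might go further and conclude that the trial cannot answer its own remodeling question. That is too strong. The stated aim is to characterize, no hypothesis or success rule is attached, the paired data are collected, and further analyses are expected. The primary safety and efficacy endpoints are unaffected.

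**What to change.** In SAP 7.11 (Outcome #6) and 7.12 (Outcome #7), keep the planned visit summaries. For each CMR measure and each SF-36 scale, add the change from pre-implant at every scheduled follow-up visit, in subjects with both values:
- number of pairs, mean change, SD of change and two-sided 95% CI;
- the pre-implant mean of those same subjects, beside the mean of all subjects with a pre-implant value, so that any difference in composition is visible.

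State in Outcome #6 that 2-year and 5-year CMR are summarised separately, as in the protocol.

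Paired change describes those who remain under observation and does not remove selection. If attrition proves material, a repeated-measures model could be added as support, but it is optional.

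The cost is a short SAP edit and a few extra table columns. No new data, visits or subjects are needed.

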#### 7.12 Health outcomes

#### Outcome Measure #7: Characterize quality of life scores over time

Quality of life will be assessed by the subjects completing the RAND 36-Item Short Form (SF-36) questionnaire. Completion of the SF-36 questionnaire is required at the following intervals: pre-implant, 1-month post-implant, 6 months post-implant, and annually post-implant out to 5 years. The analysis cohort will be the implanted >24 hours cohort.

Summary statistics such as mean, standard deviation, minimum, median, and maximum will be provided for quality of life scores over time as assessed by the SF-36 at pre-implant, 1-month post-implant, 6 months post-implant, and annually post-implant out to 5 years.

The responses will be scored by using the 36-Item Short Form Survey (SF-36) Scoring Instructions published by Rand Corporation [2]. The scoring is a two-step process as described in Table 1 and Table 2:

Revision 5.1 Page 21 of 24

[figure not shown]

Table 1. Step 1: Recoding Items

Item numbers	Change original	To recoded
	response category *	value of:
1, 2, 20, 22, 34, 36	1 →	100
	2 →	75
	3 →	50
	4 →	25
	5 →	0
3, 4, 5, 6, 7, 8, 9, 10, 11, 12	1 →	0
	2 →	50
	3 →	100
13, 14, 15, 16, 17, 18, 19	1 →	0
	2 →	100
21, 23, 26, 27, 30	1 →	100
	2 →	80
	3 →	60
	4 →	40
	5 →	20
	6 →	0
24, 25, 28, 29, 31	1 →	0
	2 →	20
	3 →	40
	4 →	60
	5 →	80
	6 →	100
32, 33, 35	1 →	0
	2 →	25
	3 →	50
	4 →	75
	5 →	100

\* Pre-coded response choices as printed in the questionnaire.

Revision 5.1 Page 22 of 24

[figure not shown]

Table 2. Step 2: Averaging Items to Form Scales

Scale	Number of items	After recoding per Table 1,
		average the following items
Physical functioning	10	3 4 5 6 7 8 9 10 11 12
Role limitations due to physical health	4	13 14 15 16
Role limitations due to emotional problems	3	17 18 19
Energy/fatigue	4	23 27 29 31
Emotional well-being	5	24 25 26 28 30
Social functioning	2	20 32
Pain	2	21 22
General health	5	1 33 34 35 36

Table 1 shows that responses 1 through 5 for item 20 should be recoded to values of 100, 75, 50, 25, and 0, respectively. Responses 1 through 5 for item 32 should be recoded to values of 0, 25, 50, 75, and 100, respectively. Table 2 shows that these two recoded items should be averaged together to form the social functioning scale. If the respondent is missing one of the two items, the person's score will be equal to that of the non-missing item. The scale for each of 8 domains will be calculated respectively and will be counted as the quality of life score.

Summary statistics for continuous variable will be provided for the quality of life scores at pre-implant, 1-month post-implant, 6 months post-implant, and annually post-implant out to 5 years.

## 7.13 Pooled Analysis with Early Feasibility Study and Pivotal Study

The analysis population for the Harmony PMA will include subjects from the Harmony Pivotal Study in combination with the data from the Native Outflow Tract Transcatheter Pulmonary Valve Research Clinical Study (IDE #G120175), since the 2 studies have the same inclusion and exclusion criteria except for the inclusion criteria listed below. This difference in the inclusion criteria does not change the patient populations in the studies. Therefore, data can be pooled for analysis. Note the Native study only includes TPV22 implants.

Harmony Pivotal Study	Early Feasibility Study
Clinical indication for surgical placement of a RV-PA conduit or prosthetic pulmonary valve per one or more of the following criteria:	Clinical indication for surgical placement of a RV-PA conduit or prosthetic pulmonary valve per one or more of the following criteria:

 
Subject is symptomatic secondary to pulmonary insufficiency (e.g. exercise intolerance,
 
	
 
Subject is symptomatic secondary to pulmonary insufficiency (e.g. exercise intolerance,
 

Harmony Pivotal Statistical Analysis Plan	

Revision 5.1

Page 23 of 24 Medtronic

fluid overload) as classified by	fluid overload) as classified by the
the investigator, or	investigator, or

 
Right ventricular end diastolic volume index (RVEDVi) ≥ 150 ml/m², or
 
Subject has RVEDV: LVEDV Ratio ≥ 2.0
 
	
 
○ Right ventricular end diastolic volume index (RVEDVi) ≥ 150 ml/m²
 

The following endpoints will be analyzed with the pooled data sets:

- Primary Safety Endpoint: freedom from procedure or device-related mortality at 30 days post implant
- Primary Efficacy Endpoint: percentage of subjects with acceptable hemodynamic function at 6 months
- Safety Evaluation
- Technical success at exit from catheterization lab/operating room
- Device success
- Freedom from TPV dysfunction
- Characterization of right ventricle remodeling following TPV implant

